7.8 SAFETY ANALYSIS

The safety analysis will be based on the treated set (TS).

While tables will generally display results by randomised treatment, listings will reflect whether a measurement/AE occurred on or off treatment.

7.8.1 Adverse events

Unless otherwise specified, the analyses of adverse events (AEs) will be descriptive in nature and will be based on the number of patients with AEs and not on the number of AEs.

AEs will be coded using version 22.0 of the Medical Dictionary for Regulatory Activities (MedDRA) coding dictionary.

Definitions of Boehringer Ingelheim customised MedDRA Queries (BIcMQs) for new MedDRA versions are maintained by the BI dictionary maintenance group.

For analysis multiple AE occurrence data in the data from the eCRF will be collapsed into an AE provided that all of the following applies:

- All AE attributes are identical (including Lowest Level Term (LLT), intensity, action taken, therapy required, seriousness, reason for seriousness, relationship, outcome, AE of special interest and also additional information of specific AEs or AESIs such anatomical location of UTI (upper UTI kidney versus Lower UTI bladder and below versus asymptomatic bacteriuria) or type of genital infection (fungal balanitis or vulvovaginitis versus other than fungal balanitis or vulvovaginitis)).
- The occurrences were time-overlapping or time-adjacent (time-adjacency of 2 occurrences is given if the second occurrence started on the same day or on the day after the end of the first occurrence).

For further details on summarisation of AE data, please refer to [\(2\)](#).

7.8.1.1 Assignment of AEs to treatment

The analysis of adverse events will be based on the concept of treatment-emergent adverse events. That means that all adverse events occurring between first drug intake till 7 days after last drug intake will be assigned to the randomised treatment. All adverse events occurring

before first drug intake will be assigned to ‘pre-treatment’ and all adverse events occurring after last drug intake + 7 days will be assigned to ‘follow-up’, except if otherwise specified.

In Section 15.3 general AE analysis tables will present only on-treatment AEs (applying the rule of 7 days for assignment as on-treatment) for the treatment groups.

Appendix 16.1.13.1 will include an analysis (overall summary table, frequency of AEs by system organ class (SOC) / preferred term (PT), frequency of serious adverse events (SAEs) by SOC/PT) where AEs and SAEs are assigned to the following phases: Screening, each treatment group, post-treatment for each treatment group.

For listings, AEs will be assigned to one of the treatment phases of Screening, Placebo, Empa 10, Post Placebo, Post Empa.

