5.2.7.2 Adverse event collection and reporting

AE Collection

The investigator shall maintain and keep detailed records of all AEs in the patient files. The following must be collected and documented on the appropriate CRF(s) by the investigator:

- From signing the informed consent onwards until the individual patient's end of trial:
All AEs (serious and non-serious) and all AESIs.
- After the individual patient's end of trial:
The investigator does not need to actively monitor the patient for AEs but should only report related SAEs and related AESIs of which the investigator may become aware of by any means of communication, e.g. phone call. Those AEs should however, not be reported in the CRF.

[figure not shown]

Figure 5.2.7.2: 1 Adverse Event Collection Periods

AE reporting to sponsor and timelines

The investigator must report SAEs, AESIs, and non-serious AEs which are relevant for the reported SAE or AESI, on the BI SAE form via fax immediately (within 24 hours) to the sponsor's unique entry point (country specific contact details will be provided in the ISF). The same timeline applies if follow-up information becomes available. In specific occasions the investigator could inform the sponsor upfront via telephone. This does not replace the requirement to complete and fax the BI SAE form.

With receipt of any further information to these events, a follow-up SAE form has to be provided. For follow-up information the same rules and timeline apply as for initial information.

Information required

For each AE, the investigator should provide the information requested on the appropriate eCRF pages and the BI SAE form, if applicable. The investigator should determine the causal relationship to the trial medication. .

The following should also be recorded as an (S)AE in the CRF and BI SAE form (if applicable):

- Worsening of the underlying disease or of other pre-existing conditions
- Changes in vital signs, ECG, physical examination and laboratory test results, if they are judged clinically relevant by the investigator.

If such abnormalities already pre-exist prior to trial inclusion they will be considered as baseline conditions and should be collected in the eCRF only. All (S)AEs, including those persisting after individual patient's end of trial must be followed up until they have resolved, have been assessed as "chronic" or "stable", or no further information can be obtained.

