7.3.4 Safety analyses

Adverse events will be coded using the Medical Dictionary for Drug Regulatory Activities (MedDRA). Standard BI summary tables and listings will be produced. All adverse events with an onset between start of treatment and end of the residual effect period (REP), a period of 7 days after the last dose of trial medication, will be assigned to the on-treatment period for evaluation.

All treated patients will be included in the safety analysis. In general, safety analyses will be descriptive in nature and will be based on BI standards. No hypothesis testing is planned.

Statistical analysis and reporting of adverse events will concentrate on treatment-emergent adverse events, i.e. all adverse events occurring between start of treatment and end of the residual effect period. Adverse events that start before first drug intake and deteriorate under treatment will also be considered as 'treatment-emergent'.

Frequency, severity, and causal relationship of adverse events will be tabulated by system organ class and preferred term after coding according to the current version of the Medical Dictionary for Drug Regulatory Activities (MedDRA) at the database lock.

Laboratory data will be analysed both quantitatively as well as qualitatively. The latter will be done via comparison of laboratory data to their reference ranges. Values outside the reference range as well as values defined as clinically relevant will be summarised. Treatment

groups will be compared descriptively with regard to distribution parameters as well as with regard to frequency and percentage of patients with abnormal values or clinically relevant abnormal values.

Vital signs, physical examinations, or other safety-relevant data observed at screening, baseline, during the course of the trial and at the end-of-trial evaluation will be assessed with regard to possible changes compared to findings before start of treatment.

Reasons for discontinuation and use of post-baseline concomitant medications will be tabulated.

The details of the analysis will be specified in the Trial Statistical Analysis Plan (TSAP).

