4. CHANGES IN THE PLANNED ANALYSIS OF THE STUDY

4.1 CHANGES NEWLY INTRODUCED FROM THE CLINICAL TRIAL PROTOCOL

Analyses of the following endpoints have been added:

- Systolic blood pressure
- Diastolic blood pressure
- Body weight

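### SAP 7.8.1.1 omits, without declaring it, the protocol rule that adverse events starting before first intake and worsening on treatment count as treatment-emergent

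*SAP*

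**What the plan says.** Protocol 7.3.4 (Safety analyses) defines treatment-emergent AEs in two parts. The first is a time window: "all adverse events occurring between start of treatment and end of the residual effect period", where that period ends 7 days after the last dose. The second is a worsening rule: "Adverse events that start before first drug intake and deteriorate under treatment will also be considered as" treatment-emergent.

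SAP 7.8.1.1 says the AE analysis rests on the treatment-emergent concept and then spells out what that means. AEs from first intake to 7 days after last intake go to the randomised treatment. AEs "before first drug intake will be assigned to" the pre-treatment category. Later ones go to follow-up, "except if otherwise specified". On presentation it states: "In Section 15.3 general AE analysis tables will present only on-treatment AEs".

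SAP 4.1, the list of departures from the protocol, begins "Analyses of the following endpoints have been added" and names only systolic and diastolic blood pressure and body weight.

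Protocol 5.2.7.2 has AEs collected as follows: "From signing the informed consent onwards until the individual" patient's end of trial. Among the things to be recorded as an AE it lists: "Worsening of the underlying disease or of other pre-existing conditions".

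**The concern.** The SAP claims the protocol's concept but carries over only half of its definition. AEs are collected from consent and screening can last up to three weeks (Protocol 3.1), so some patients will start study drug with an AE already open. If such an AE then becomes severe or serious on study drug, the protocol says it belongs to the treatment period. Under the SAP's written rule it belongs to the period before treatment.

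The Section 15.3 tables are where a reader compares the arms on safety. An event that worsened on drug but is filed under Screening does not enter that comparison. The change is also undeclared, so a reader who knows the protocol would assume that the tables include such events.

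**Working it through.** The plan gives no figure on this point. The check is a comparison of texts, followed by one consistency check on a SAP formula.

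**1. The two definitions side by side**

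| Case | Protocol 7.3.4 | SAP 7.8.1.1 |
|---|---|---|
| AE begins between first intake and last intake + 7 days | Treatment-emergent | Randomised treatment |
| AE begins before first intake, does not worsen | Not treatment-emergent | Pre-treatment |
| AE begins before first intake, worsens on treatment | Treatment-emergent | Pre-treatment; no exception stated |

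The documents agree on the first two rows and differ on the third.

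**2. Is an exception specified elsewhere?** SAP 7.8.1.1 leaves room for one in general terms, but the SAP's AE sections (7.8.1 to 7.8.1.7) give none for worsening. Neither SAP 4.1 nor the SAP history table mentions a change to the definition.

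**3. Does the incidence-rate formula allow for such an AE?** SAP 7.8.1.7 sets, for a patient with the AE,

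time at risk (days) = AE start date − treatment start date + 1.

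Illustrative onsets before first intake give:

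- onset 1 day before: −1 + 1 = 0 days;
- onset 5 days before: −5 + 1 = −4 days;
- onset 21 days before (the earliest screening day in the flow chart): −21 + 1 = −20 days.

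Every pre-treatment onset gives a zero or negative time at risk. The formula uses no date of worsening. Adding these AEs to the on-treatment tables without changing the formula would therefore give meaningless contributions to the denominator. This agrees with the reading that the SAP was written without the worsening rule.

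**4. Where does the AE end up?** That depends on how the site records it.

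- *Worsening entered as a new record with its own on-treatment onset.* SAP 7.8.1 merges occurrences only when all attributes match, including intensity and seriousness, so the new record stays separate. It falls in the treatment window and is counted in Section 15.3.
- *One record kept, with the pre-treatment onset and an updated intensity or seriousness.* SAP 7.8.1.1 assigns it to pre-treatment. It is absent from Section 15.3. It appears under Screening in Appendix 16.1.13.1 and in the listings.

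The documents do not say which of these the eCRF requires for an AE already open at first intake.

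**The case against.** The best defence is that silence is not repeal. SAP 3 says the SAP is based on Section 7 of the protocol, which contains the worsening rule; SAP 7.8.1.1 invokes the same concept; it speaks of AEs occurring, not starting, before first intake; and it allows for exceptions. On that view, the absence of an entry in SAP 4.1 shows that the protocol rule still stands. This has some force: an analyst could read the rule in. But the SAP does more than stay silent. It states what the concept means, gives only the time window, sends everything earlier to pre-treatment, and uses a time-at-risk formula that cannot accommodate the omitted case. Protocol 7.3.4 leaves the details of the safety analysis to the SAP, so the written SAP rule is the one likely to be programmed.

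The second defence is that the usual route is covered. Worsening of pre-existing conditions is recordable as an AE, and records that differ in intensity or seriousness are not merged. This stands, and it confines the problem to AEs kept as one record.

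A reader might infer something stronger: that hypotension, renal decline or urinary infection beginning in screening and worsening on drug would be lost from the safety report. The documents do not support that.

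- An acute urinary infection at screening is documented as medical history or a baseline condition (Protocol 5.2.4.4), so later worsening is recordable as an AE in its own right.
- Symptomatic hypotension at Visit 1 or 2 is an exclusion (Protocol 3.3.3, criterion 6).
- Renal decline is also captured by the creatinine frequency tables (SAP 7.8.1.3) and by the eGFR shift table to the minimum on-treatment value (SAP 7.8.2), whatever the AE onset.

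An AE kept as one record also remains in Appendix 16.1.13.1 and the listings. It is missing from the on-treatment tables, not from the report.

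**Conclusion.** The point holds as an inconsistency between protocol and SAP with a limited consequence. SAP 7.8.1.1 leaves out a rule that Protocol 7.3.4 states explicitly, and the departure is not declared. An AE with pre-treatment onset that worsens on drug can be absent from the Section 15.3 tables if it is held as one record.

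The number of such events cannot be estimated: the documents give neither a screening AE rate nor the eCRF convention for worsening. It is probably small. Screening is at most about three weeks, patients must be clinically stable at randomisation, and only the single-record case is affected. With about 150 patients per arm, one or two added serious events could still be visible in a table row.

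No primary or key secondary result is touched. The safety analyses are descriptive, without hypothesis tests.

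The conclusion assumes that the SAP is programmed as written and that at least some sites update an open AE and do not enter a new one. If the eCRF instructions require a new record at every worsening, nothing is lost in practice and only the wording needs correcting.

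**What to change.** In SAP 7.8.1.1, restate the rule from Protocol 7.3.4: an AE that starts before first intake and deteriorates under treatment is assigned to the randomised treatment.

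State how worsening is identified. Use a separate AE record with its own onset date where one exists. Where none exists, use a blinded review of AEs ongoing at first intake.

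In SAP 7.8.1.7, use the recorded date of worsening as the event date where it is available. Where it is not, apply a stated convention, for example the date of first intake, which gives 0 + 1 = 1 day at risk in place of a zero or negative value. The convention is needed because the source-document list in Protocol 8.3.1 names only onset and end dates for AEs. It should not be assumed that a date of intensity change is in the database.

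If the sponsor does intend to drop the rule, declare and justify the departure in SAP 4.1.

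The cost is a short SAP revision, a limited blinded review, and approximate timing for AEs with no recorded date of worsening.

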7.8.1.2 AE summaries

An overall summary of adverse events will be presented.

The frequency of patients with adverse events will be summarised by treatment, primary system organ class and preferred term. Incidence rates as defined in [Section 7.8.1.7](#) will generally be included.

AEs will also be reported by intensity (without incidence rates). Separate tables will be provided for

- for patients with serious adverse events,
- for patients with drug related serious AEs,
- for patients with AEs leading to discontinuation
- for patients with drug-related AEs.

AEs leading to death will be listed.

The system organ classes will be sorted according to the standard sort order specified by the European Medicines Agency (EMA), preferred terms will be sorted by frequency (within system organ class).

Additionally, the following analyses will be reported in Appendix 16.1.13.1 for disclosure on EudraCT and clinicaltrials.gov:

- Frequency [N(%)] of subjects with non-serious adverse events occurring with incidence in preferred term greater than 5% by treatment,
- Adverse events per arm for disclosure on EudraCT by treatment
- Non-serious adverse events for disclosure on EudraCT by treatment
- Serious adverse events for disclosure on EudraCT by treatment

7.8.1.3 Adverse events of special interest (AESIs)

Hepatic injury

Hepatic injury AEs will be summarised based on a Standardised MedDRA Query (SMQ) based definition. From SMQ Drug related hepatic disorders (20000006) the following narrow sub-SMQs will be used:

- Narrow sub-SMQ Liver related investigations, signs and symptoms (20000008)
- Narrow sub-SMQ Cholestasis and jaundice of hepatic origin (20000009)
- Narrow sub-SMQ Hepatitis, non-infectious (20000010)
- Narrow sub-SMQ Hepatic failure, fibrosis and cirrhosis and other liver damage-related conditions (20000013)

A table with frequencies of patients with these AEs by treatment, primary SOC and preferred term will be provided. Hepatic injury SAEs based on the above SMQ definition will be presented.

Patients with hepatic injury will be listed.

For presentations on adjudicated hepatic events, refer to [Section 7.8.1.5](#).

Acute renal failure

A frequency table of patients with AEs related to acute renal failure by treatment, primary SOC and preferred term will be provided based on the narrow SMQ Acute renal failure (20000003).

SAEs and AEs leading to discontinuation based on the narrow SMQ Acute renal failure (20000003) will be presented.

In addition, frequency tables will be produced for patients with elevated creatinine ≥ 2 x baseline and > 1 x upper limit of normal (ULN).

Patients with acute renal failure will be listed.

Ketoacidosis

A frequency table of patients with AEs related to ketoacidosis will be presented by treatment, primary SOC and preferred term for investigator reported cases and for the narrow and broad BICMQ definition of diabetic ketoacidosis (DKA).

For presentations on adjudicated events, refer to [Section 7.8.1.5](#).

Patients with DKA based on the broad BICMQ (30000019) or investigator reported ketoacidosis will be listed.

7.8.1.4 Specific AEs

Hypoglycaemic events

The investigator will record for each AE whether it represents a hypoglycaemic event and, if so, record additional information to assess the intensity of the hypoglycaemic event. On the basis of this information the hypoglycaemic event will be categorised as follows:

- severe hypoglycaemic episode: event requiring the assistance of another person to actively administer carbohydrate, glucagon or other resuscitative actions
- documented symptomatic hypoglycaemia with a measured plasma glucose concentration < 3.0 mmol/L (< 54 mg/dL): event accompanied by typical symptoms of hypoglycaemia but no need for external assistance
- documented symptomatic hypoglycaemia with a measured plasma glucose concentration ≥ 3.0 mmol/L and ≤ 3.9 mmol/L (≥ 54 mg/dL and ≤ 70 mg/dL): event accompanied by typical symptoms of hypoglycaemia and no assistance required
- symptomatic hypoglycaemia and plasma glucose concentration > 3.9 mmol/L (70 mg/dL)
- symptomatic hypoglycaemia and plasma glucose concentration not measured
- asymptomatic hypoglycaemia: event not accompanied by typical symptoms of hypoglycaemia but with a measured plasma glucose concentration ≤ 3.9 mmol/L (≤ 70 mg/dL)

Confirmed hypoglycaemic adverse event are defined as hypoglycaemic adverse events that had a plasma glucose concentration ≤ 70 mg/dL or required assistance.

Different tables will be shown for (i) patients with investigator-defined hypoglycaemia, and (ii) patients with confirmed hypoglycaemic adverse events, i.e. hypoglycaemic adverse events that had a plasma glucose concentration ≤ 70 mg/dL or required assistance.

Subgroup analyses on confirmed events with respect to DM status at baseline (DM vs non-DM) will be performed.

In addition the number of patients with hypoglycaemia according to SMQ (20000226) will be presented.

Patients with hypoglycaemic events will be listed.

Urinary tract infections (UTI) and genital infections

The following additional specific adverse events will also be assessed and be tabulated by treatment group:

- Genital infections (BICMQ “Infections” (30000036) narrow subsearch 1.1 “Genital tract infections predisposed to by glucosuria” (30000038) and investigator assessment)

- UTI (BICMQ “Infections” (30000036) narrow subsearch 2.1 “UTI predisposed by glucosuria” (30000041) and investigator assessment)

Genital infections based on investigator assessment will additionally be summarised by type (fungal balanitis or fungal vulvovaginitis, genital infection other than fungal balanitis or fungal vulvovaginitis), intensity (mild, moderate or severe), how the event was treated (no treatment, therapy assigned and number of antimicrobials needed to treat), whether leading to discontinuation of treatment, and the number of episodes per patient.

UTIs based on investigator assessment will additionally be summarised by intensity (mild, moderate or severe), anatomical location (upper UTI, lower UTI), occurrence of pyelonephritis or urosepsis, how the event was treated (no treatment, therapy assigned and number of antimicrobials needed to treat), whether leading to discontinuation of treatment, and the number of episodes per patient.

Complicated urinary tract infections defined as serious adverse events of BICMQ Infection narrow, subsearch 2.1 “UTI predisposed by glucosuria” (30000041), all events of subsearch 2.1.1 ‘Renal infections predisposed by glucosuria’ (30000042), all events of PT Urosepsis will be presented.

Complicated genital infection: defined as all serious events using the BICMQ Infection narrow subsearch 1.1 ‘Genital tract infections predisposed to by glucosuria’ (30000038) and all event of the subsearch ‘Complicated genital tract infections predisposed to by glucosuria’ (30000129) will also be presented.

Patients with UTIs or genital infections will be listed.

Bone fracture events:

Frequency tables of patients with bone fracture by treatment, primary system organ class (SOC) and preferred term will be provided (based on the narrow BICMQ “Bone fractures” (30000008) and investigator reporting).

Investigator reported fractures will be reported overall and separately for each type of fracture (traumatic and non-traumatic).

Separate tables for bone fractures based on the BICMQ, which are serious will be presented.

Patients with bone fractures will be listed.

Urinary tract malignancy events:

Urinary tract malignancy will be shown based on the BICMQ ‘Malignancies’ (30000049) – broad sub-search 14.1 ‘Urinary bladder and tract malignancies’ (30000057) and broad sub-search 14.2 ‘Renal malignancies’ (30000103):

Presentation of frequency will be done by treatment, high level term and preferred term.

Patients with urinary tract malignancy will be listed.

Volume depletion

Volume depletion will be based on the BICMQ ‘Volume depletion of non-haemorrhagic cause and subsequent hypotension’ – narrow subsearch 2 ‘Volume depletion and hypotension due to dehydration’ (30000090).

A frequency table of patients with volume depletion by treatment, primary SOC and preferred term will be provided.

A separate table for serious volume depletion events will be presented.

Patients with volume depletion will be listed.

For the analysis of laboratory data, refer to [Section 7.8.2](#).

Hypotension:

Frequency table of subjects with symptomatic hypotension as defined by the investigator on the eCRF tick box by treatment, primary system organ class and preferred term will be provided.

Symptomatic hypotension episodes will be presented by whether the intensity of diuretic medication was reduced and by whether the intensity of non-diuretic antihypertensive therapy was reduced.

A separate table for symptomatic hypotension events, which are serious, will be presented.

Additionally hypotension by treatment, primary system organ class and preferred term will be provided. Hypotension is defined as preferred terms of the BICMQ ‘Volume depletion of non-haemorrhagic cause and subsequent hypotension’ – narrow sub-search 2 ‘Volume depletion and hypotension due to dehydration’ (30000090) but excluding terms of the narrow subsearch 1 ‘Volume depletion due to dehydration’(30000089).

A separate table for hypotension events, which are serious, will be presented.

Patients with hypotension events will be listed.

